Appendix 4: EMS Structure Dataforms.....	154
Appendix 5: Draft Registry Dataforms.....	154

RESUSCITATION OUTCOMES CONSORTIUM REGISTRY

A. SPECIFIC AIMS

Overview

Out-of-hospital cardiac arrest and life-threatening traumatic injury are common, serious, debilitating and costly public health problems. The Resuscitation Outcomes Consortium (ROC) consists of ten Regional Clinical Centers and a Data and Coordinating Center (DCC). The University of Washington Clinical Trial Center serves as the DCC. The Consortium was funded by the National Heart Lung Blood Institute and other government agencies to conduct a series of large randomized trials to evaluate the effectiveness of interventions for these disorders. Additional funding has been obtained from the American Heart Association to offset the cost of extending ROC activities to include a registry to define the true burden of cardiac arrest. Also, the National Center for Injury Prevention and Control, Centers for Disease Control and Prevention will provide in-kind scientific expertise during the first year and may provide additional funding in subsequent years to define the true burden of life-threatening traumatic injury. These burdens are, at best, only crudely known. Whether and how EMS process, geographic, socioeconomic and periodic variation are associated with differences in outcome is unknown. This can be largely attributed to the absence of any internationally-representative epidemiologic database that includes outcome. Since patients at higher risk of poor outcomes are often excluded from clinical trials, estimation of the burden of illness based on those enrolled in ROC trials is subject to bias. Knowledge of factors related to specific episodes, together with regional factors including EMS system factors and outcome is a first step toward the development, implementation and evaluation of interventions to improve outcomes associated with these illnesses.

The overall goal of the proposed study is to supplement our existing DCC grant to implement a comprehensive and ongoing data infrastructure during the remaining four years of ROC activities, and to extend the work of ROC to include an EMS-based registry of out-of-hospital cardiac arrest and life-threatening traumatic injury in participating ROC sites to facilitate the ROC interventional trials. The DCC was aware of the potential value of a ROC Registry (and discussed it in our original coordinating center application) because of our previous experience with the use and value of registries alongside clinical trials (e.g., CAST trial, AVID trial). In both cases, the registries facilitated the efficient conduct of the trials, interpretation of their results, and were a rich source of data for hypothesis generation. However, the necessity of a ROC Registry has only become apparent since the sites and coordinating center for this trials network were selected and began to work out the details for proposed intervention trials. It has become clear that the effort required to set in motion the infrastructure for conducting and collecting EMS data is far more complex than that of other clinical trials and once in place is far more efficient to continue between protocols.

Aims of the Registry are to establish whether the results of ROC trials can be generalized to the population at large that experiences cardiac arrest or traumatic injury; to more fully establish the burden of these illnesses; the relationship between variation in EMS structure and process, regional factors such as geographic area or socioeconomic status, periodic factors and outcome. Included will be patients who experience out-of-hospital cardiac arrest or life-threatening traumatic injury and are evaluated by organized emergency response personnel at any level. For the purposes of this study, the designation Emergency Medical System (EMS) includes any and all levels of organized emergency response. We anticipate that participating sites serve a population of about 24,500,000 and will enroll about 17,500 cases of cardiac arrest and about 13,000 cases of trauma with impaired physiology in the field annually. Estimated survival to discharge will be 5.57% after cardiac arrest. Estimated mortality will be 16.55% after trauma with impaired physiology in the field. With these incidence and outcome rates, we will have 88%, 90%, 99% and 91% power to detect risk differences of 2.5/100,000 in the annual rate of cardiac arrest, 2.5/100,000 in the annual rate of traumatic injury, 1% in survival to discharge after cardiac arrest, and 1.5% in mortality after traumatic injury.

SPECIFIC AIM 1

To establish a comprehensive ongoing data infrastructure to facilitate the design, implementation and interpretation of ROC trials.

Hypothesis 1: The null hypothesis is that the characteristics of enrolled and non-enrolled patients are identically distributed.

SPECIFIC AIM 2

To define the incidence and outcome of out-of-hospital cardiac arrest and life-threatening traumatic injury.

Hypotheses 2a: The null hypotheses are that the EMS-based incidence of cardiac arrest and injury are identically distributed from year to year.

Hypotheses 2b: The null hypotheses are that the survival to hospital discharge after cardiac arrest and for injury are identically distributed from year to year.

SPECIFIC AIM 3

To describe the relationships between resuscitation performance and EMS structure, adjusting for episode-specific factors.

Hypotheses 3a: The null hypotheses are that the EMS process of care and structure for cardiac arrest and injury are identically distributed from agency to agency, both before and after adjustment for episode-specific factors.

Hypotheses 3b: The null hypotheses are that the EMS process of care and structure for cardiac arrest and injury are identically distributed from year to year, both before and after adjustment for episode-specific factors.

SPECIFIC AIM 4

To evaluate the relationships between outcome and patient, EMS, regional, and periodic factors.

Hypotheses 4a: The null hypothesis are that EMS structures will not be predictive of outcome, after adjustment for episode-specific factors including resuscitation performance.

Hypotheses 4b: The null hypotheses are that geographic and socioeconomic factors will not be predictive of outcome, after adjustment for episode-specific factors.

Hypotheses 4c: The null hypotheses are that circadian and seasonal factors will not be predictive of outcome, after adjustment for episode-specific and regional factors.

B. BACKGROUND AND SIGNIFICANCE

Overview of the Resuscitations Outcomes Consortium (ROC)

The Resuscitation Outcomes Consortium was established in 2004 by the National Heart Lung and Blood Institute of the National Institute of Health, in partnership with the Institute of Circulatory Respiratory Health of the Canadian Institutes of Health Research and other agencies. The goal of the ROC is to conduct clinical research in the areas of cardiopulmonary arrest and life-threatening traumatic injury. The ROC has the necessary infrastructure to conduct multiple randomized trials to aid rapid translation of promising scientific and clinical advances to improve resuscitation outcomes. Our focus on prehospital interventions recognizes the common epidemiology and physiology of cardiac arrest and trauma, as well as the time-dependent nature of treatment of these disorders.

Clinical trials will evaluate existing or new therapies (such as pharmacologic interventions, strategies of fluid resuscitation, or the use of immune modulators), clinical management strategies (such as bleeding control strategies, the use of cerebral protection, metabolically-directed therapies, and alternative CPR approaches), or a combination of the two. Consortium investigators will conduct trials of variable size and duration (equally

directed towards the cardiac and trauma populations). The ROC has an initial commitment of five years of funding, with a possibility of renewed funding.

Need to Facilitate ROC Intervention Trials

Baseline data submitted by the participating ROC sites demonstrate large and potentially important variations in the incidence and outcome of cardiac arrest and major trauma as well as EMS practices used to treat them. Failure to control for factors that account for some of these differences will increase the sample size of and may bias or confound the results of ROC intervention trials. For example, ROC investigators are currently designing a trial to assess the effect of an impedance threshold valve that is intended to increase venous return during cardiopulmonary resuscitation (CPR). Provision of good CPR is likely necessary to optimize the effect of the valve, but some ROC sites train their providers to analyze and defibrillate as quickly as possible whereas others train them to provide CPR for at least 90 seconds before analysis and shock. Non-random distribution of early analysis versus late analysis, or other differences in EMS process, among patients participating in the trial of the valve would reduce our ability to detect whether it is effective. Randomization of individual episodes of cardiac arrest to early analysis versus late analysis is not feasible due to the emergent nature of the event. The loss of compliance caused by the confusion of having an EMS provider alternate between the basic concept of assiduously assessing rhythm and defibrillating initially or aggressively doing CPR initially can be easily appreciated. Indeed a previous trial in the out-of-hospital setting confirmed that individual randomization of episodes to alternate treatment strategies can be associated with a high rate of protocol violations due to contamination or crossover.(1)

An alternate approach to controlling for differences in EMS process across ROC agencies is to allocate the same intervention(s) to clusters or groups of patients. For example, ROC investigators are currently designing a cluster randomized trial to assess the effect of an early analysis versus late analysis using EMS agencies as the cluster unit. Cluster randomization or randomization of individual episodes both require unbiased identification of whether patients are eligible. Since all episodes in a cluster receive the same intervention, ascertainment of 100% of episodes is necessary to prevent such bias. Similar arguments can be made for ascertainment of major trauma episodes. At present no ROC EMS agency has the infrastructure in place to capture all out-of-hospital cardiac arrest and major trauma episodes. Therefore a registry is necessary to establish a streamlined and persistent method of episode notification to reduce the potential for bias in ROC intervention trials.

Burden of Illness

Sudden Cardiac Arrest (SCA) – It is unclear how often cardiac arrest occurs. Most sources state about 400,000 to 460,000 Americans per year.(2, 3) However many of these are not treatable. Among participating ROC sites, there is a two-fold variation in the incidence of cardiac arrest. These differences may reflect lack of a commonly applied definition of cardiac arrest, or incompleteness of episode identification. A community-wide study in Oregon suggests that 0.53 sudden deaths occur per 1000 population annually.(4) The incidence of cardiac arrest treated by emergency medical services (EMS) is 0.57 per 1000 population in Canada.(5) Together these data suggest that about 180,000 treatable cardiac arrests occur each year in North America (US population 295,483,056 X 0.53 per 1000 population X 1.05 since 5% survive + Canadian population 31,127,234 X 0.57 per 1000 population).

Globally, cardiovascular disease contributes 30.9% of overall mortality and 10.3% of the burden of disease.(6-8) It is responsible for more deaths than any other disease in industrialized countries, and three-quarters of mortality due to non-communicable diseases in developing countries. Eighty per cent of deaths due to cardiovascular disease occur in low- and middle-income countries. In the United States, cardiovascular disease is the leading cause of death among individuals of any age, as well as those aged greater than 65 years, second leading cause of death among individuals aged 0 to 14 years and 45 to 64 years, and fourth leading cause of death among individuals aged 15 to 24 years (www.americanheart.org/downloadable/heart/1103834819155FS23LCD5.pdf accessed on March 2, 2005). Cardiovascular disease is projected to cost \$368 billion in 2004 (<http://nhlbi.nih.gov/about/03factbka.pdf> accessed on October 22, 2004).

There has been a steady decline in morbidity and mortality from most cardiovascular diseases over the last 30 years.(9-11) The majority of this reduction has been attributed to risk factor modification.(12) Unfortunately, there has been little improvement in survival from SCA.(13, 14) Only 6.4% of affected individuals survive to discharge.(15) In summary, cardiac arrest continues to be a common, lethal, debilitating and costly disorder in North America and the rest of the world.

Life-Threatening Trauma- The true incidence of traumatic injury is also elusive. Among participating ROC sites, there is a four-fold variation in the incidence of major trauma and five-fold variation in the incidence of trauma with impaired physiology in the field. These differences may reflect lack of a commonly applied definition of trauma, or incompleteness of episode identification. Hospital-based data from the Centers for Disease Control suggest that in the United States the incidence of fatal injuries due to any injury is 55 per 100,000; the incidence of non-fatal injuries is 10,500 per 100,000 (<http://webappa.cdc.gov/cgi-bin/broker.exe> accessed on October 22, 2004) 13,750 Canadians died due to injuries in 1999 (http://www.phac-aspac.gc.ca/injury-bles/facts_e.html accessed on February 16, 2005). Together these data suggest that about 175,000 fatal injuries occur each year in North America (US population 295,483,056 X 55 per 100,000 population).

Globally, injury contributes 10% mortality.(16) It is the leading cause of death among individuals aged less than 24 years in industrialized countries,(17) and in over half the countries that report statistics.(7) In the US, injury is associated with greater years of potential life lost than any other target disorder. Trauma is the leading cause of death among individuals aged one to 44 years, and third leading cause among individuals aged 44 years to 54 years (<http://webappa.cdc.gov/cgi-bin/broker.exe> accessed on August 23, 2005). Injuries were responsible for 2.6 million hospitalizations, and 37 million emergency room visits.(18) The majority of these are due to either motor vehicle accidents or intentional injury with firearms. Among patients treated in level I-V trauma centers in the US and reported to the National Trauma Registry, 65% suffer minor injuries, 1% die in the emergency department and overall the mortality is 4.6% (<http://www.facs.org/trauma/ntdb/ntdbannualreport2004.pdf> accessed Oct 26, 2004). The actual societal burden from trauma is likely to be substantially higher when estimates include deaths at the scene of injury,(19) deaths in the emergency department and during hospitalization, deaths following hospitalization that are attributable to injury (20) as well as morbidity and reduced quality of life among certain survivors. (21) Societal costs of vehicular injury-related morbidity and mortality is projected to cost \$257 billion in fiscal year 2005.(22)

Previous reports suggest an overall decline in mortality due to trauma.(23, 24) However, recent American data suggest that mortality from blunt trauma through motor vehicle accidents has increased since the national maximum speed limit was repealed in 1995,(18) especially in rural settings.(19) By the year 2020, injury is projected to be the third leading cause of morbidity worldwide.(25) In summary, traumatic injury continues to be a common, lethal, debilitating and costly disorder in North America and the rest of the world.

Variation in Cardiac Arrest and Trauma Incidence, EMS Process and Outcome

There is a wide variation in outcomes after the onset of cardiac arrest.(15, 26) Among participating ROC sites, there is a three-fold variation in survival after cardiac arrest. This is attributable in part to regional differences in the availability of out-of-hospital and hospital-based emergency cardiac care throughout the US.(26) Interventions for cardiac arrest include: bystander CPR, lay responder defibrillation programs(27), experience of EMS providers (28), and interventions provided by EMS providers (29, 30) or at receiving hospitals (31, 32). However, only lay responder defibrillation and therapeutic hypothermia have been shown in randomized trials to improve significantly outcomes to hospital discharge after cardiac arrest.

There is substantial regional variation in EMS structures and processes, e.g., EMS service level provided, number of EMS providers responding, use of procedures or drugs in field, training, quality assurance/feedback, and response time intervals. Some of these factors have been associated with differences in survival or quality of life after resuscitation,(15, 33-36) although no analysis has had adequate power to detect independent effects of all factors. Recent technology can quantify individual episodes on such parameters as defibrillation attempts, chest compression rate, ventilation rate, and other prehospital procedures performed.(37) However, there are no published data that demonstrate significant associations between these factors and patient outcomes. Feedback of this knowledge is essential to care delivery since

improved quality assurance has been associated with improved outcomes after resuscitation.(33) Also it is essential to efficient trial conduct since low baseline rates of survival are associated with larger sample sizes to detect a clinically important difference.

There is a wide variation in outcomes after the life-threatening trauma.(24, 38) Among participating ROC sites, there is a three-fold variation in mortality after major trauma and more than two-fold variation in mortality after trauma with impaired physiology in the field. This is attributable in part to differences in the regional availability of out-of-hospital and hospital-based trauma care throughout the US.(39) For trauma patients, out-of-hospital interventions may include: airway management, fluid resuscitation, hemorrhage control and rapid transport to a trauma center. Standard treatments used in trauma centers focus on limiting blood loss, restoring perfusion, limiting secondary brain injury, and modulating the inflammatory response that leads to multiorgan failure. The effectiveness of each component of trauma resuscitation is unclear.(23, 40-47) Experts have advocated full implementation of regional trauma systems(48) that triage patients with out-of-hospital characteristics predictive of poor prognosis(49-54) to trauma centers with special expertise.

Disparities in incidence and outcomes for cardiac arrest and trauma are observed across socioeconomic gradients as well as across geographic region.(55-61) Cardiovascular disease is the leading cause of income-related differences in premature mortality in the United States,(62) and Canada,(63) Also the burden of injury is greatest among individuals of low socioeconomic status.(64) Non-Hispanic blacks bear a disproportionate burden of morbidity and mortality due to cardiovascular disease and injury.(65) These disparities may be caused by differences in genetic risk, health behaviors, educational attainment, socioeconomic disadvantage, access to preventive care, or other yet to be identified variables. As understanding of the magnitude and cause of these disparities increases, potential interventions include culturally-appropriate public health initiatives, community support and equitable access to quality care.

The incidence and outcome of cardiac arrest and trauma vary by time of day, day of week or season.(66-70) Potential interventions include raising awareness about falls or vehicular accidents and promoting safety practices during the high-frequency seasons, or resource allocation of EMS and hospital resources to match anticipated need.

In summary, cardiac arrest and trauma incidence and outcome vary widely; adequately-powered analyses of observational data can identify promising EMS interventions for these disorders. Such analyses can also yield insight into the cause of geographical, socioeconomic or time-dependent gradients in cardiac arrest or trauma, and interventions to reduce these gradients.

Significance of Proposed Project

The ROC Registry will collate high-quality comprehensive EMS-based data using uniform standardized criteria to describe structure, process and outcome for consecutive cases of cardiac arrest and injury in the 11 diverse consortium sites providing a cross-sectional view of clinical and demographic characteristics of resuscitation in greater detail than could be obtained by single-center studies or national health statistics. The process of doing this and the resulting database will provide:

1) An ongoing data collection for efficient ROC trial design, implementation and interpretation

Enrollment in each ROC trial can be monitored with a streamlined and persistent method of cardiac arrest and injury episode notification in place. Timely identification of patients eligible but not enrolled in ROC trials will allow feedback to providers regarding missed patient enrollment and hence provide for timely corrective measures to enhance enrollment and shorten the time required to complete a given study. As well, comparison of the characteristics of patients enrolled and not enrolled in ROC trials will inform the generalizability of ROC intervention trial results to the community at large that experiences out-of-hospital cardiac arrest or major trauma.

2) Unbiased Estimates of Incidence and Outcome

EMS Structure and Process Factors

The Registry will facilitate comparison of outcomes relating differing resuscitation practices in the US and Canada. This information could inform standards and education policy, as well as local EMS agency decisions. Furthermore, participating EMS systems and hospitals will receive anonymized quality assurance reports at least quarterly that will allow them to compare their own patient population, interventions and outcomes with the range among others with similar or different characteristics. Collectively, these strategies will enable clinicians and centers to identify opportunities to improve quality of care and thereby improve outcomes after cardiac arrest or traumatic injury.

Geographic and Socioeconomic Factors

Population-level information from the Registry can inform public institutions of the efficacy of local education, safety enforcement and engineering initiatives and provide an evaluation of the impact of policy changes. Examples where epidemiological data could be helpful include: bystander CPR; distribution of AED programs; community education to encourage voluntary adoption of safe behavior; enforcement of safety regulations; efficacy of engineering interventions such as seat belts, helmets or airbags, and mandatory reporting of domestic violence.

3) Relationships between EMS Structure and Process and Resuscitation Performance

Knowledge of such relationships will inform education and training as well as implementation decisions.

4) Prediction of Outcome based on Patient, EMS, Regional and Periodic Factors

Identification of prognostic or treatment factors accounting for variations in survival will generate hypotheses and result in the identification of novel interventions to evaluate in a subsequent trial by the ROC Investigators. The ability to predict variation in outcome will facilitate efficient (fewer numbers to obtain desired power) design and implementation (knowledge of key variables to control/collect) of ROC trials.

C. PRELIMINARY STUDIES AND PILOT WORK

Overview

The ROC Registry Working Group was formed in September, 2004. Activities to date have included: review of previous relevant registries; derivation of data sets that include mandatory, desirable and optional elements that describe structure, process and outcome related to EMS care for those with cardiac arrest or traumatic injury; development of consensus definitions for controversial elements in these data sets; assessment of baseline estimates of cardiac arrest and trauma incidence and outcome; and development of site-specific implementation strategies.

Relevant Cardiac Arrest or Traumatic Injury Registries

Existing cardiac arrest and trauma registries do not contain the necessary information to determine which interventions are effective in the out-of-hospital setting. For example, the National Registry for Cardio Pulmonary Resuscitation was developed in the United States to collate SCA data describing in-hospital events.⁽⁷¹⁾ As of January 1, 2005, this registry describes more than 60,000 in-hospital events that required some form of resuscitation. More than 5,000 adult and 200 pediatric events are added to the registry quarterly by > 300 participating hospitals. However, events that occur out-of-hospital are excluded from this database.

For trauma, the American College of Surgeons supports a trauma registry that only collates data describing patients transported to Level I trauma centers. The Centers for Disease Control previously developed software to support a similar registry but this does not require inclusion of consecutive cases of patients in the out-of-hospital setting. Similarly, the Canadian Trauma Registry abstracts limited EMS data and collects data on patients who are treated at a designated trauma center. The Centers for Disease Control and Consumer Product Safety Commission jointly support the National Electronic Injury Surveillance System All Injury Program (NEISS) which is a national probability sample of hospitals in the U.S. and its territories. Patient information is collected from each NEISS hospital for every emergency visit involving an injury associated with consumer products. But this survey does not include those injured without consumer products. Data that have been previously collected in other settings lack detailed information about which

interventions were administered in the prehospital setting.(24, 46, 72-74) In addition, existing trauma registries have different inclusion criteria, are not population-based, usually only include trauma centers, lack detailed EMS information, have large variability in definitions for information that is collected, and do not capture out-of-hospital deaths, all of which contribute to selection bias, difficulty in interpreting results and underestimation of the true burden of injury. Due to these limitations in existing registries, there is insufficient data to describe variation in practice and outcomes after resuscitation in different EMS agencies.

The National Highway and Traffic Safety Agency (NHTSA) has supported the development of standardized data elements to describe structure and process related to EMS care (www.nemsis.org). Although each state's EMS director has committed to collecting these data elements, there is no secure and confidential method of collating information into a single dataset. The NEMSIS data elements do not include status at hospital discharge, which is critical to ascertain the burden of illness, the outcomes of interventions trials, or the quality of EMS practices.

International consensus panels comprised of resuscitation experts have developed templates for reporting outcomes after cardiac arrest (75) or trauma.(76) However these templates have not been universally applied in multiple sites. Until recently, the cardiac arrest template lacked simple and universal operational definitions of structure, process and outcome.(77)

In summary, existing registries contained insufficient data to describe out-of-hospital structure and process, lacked operational definitions for each variable, or lacked hospital outcome data.

Consensus Development of ROC Registry Data Elements

Using the information obtained through review of the above registries, the working group identified a comprehensive list of variables that potentially would be important for a registry of out-of-hospital cardiac arrest or traumatic injury episodes. Each variable was reviewed and identified as mandatory, desirable, optional or unnecessary. Consensus definitions and response options were developed by the working group for each of the mandatory, desirable and optional variables (Appendix 1). Since EMS agencies within the United States have committed to adopting NEMSIS data initiatives, its uniform definitions and response options were used where feasible. The Utstein glossary and template for uniform reporting of out-of-hospital cardiac arrest were also incorporated where feasible. The working group modified definitions where necessary for clarification and ease of data collection. Modifications made to key definitions are summarized below:

Arrest of Cardiac Etiology

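### The stated 90% power for trauma incidence does not follow from the stated cases and population (it is about 96 to 97%), and Table 1's Pittsburgh trauma row contradicts the planning mortality

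*Protocol*

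**What the plan says.** The overview in Section A (Specific Aims) describes the catchment in these terms: "participating sites serve a population of about 24,500,000". For the yearly yield, it expects that these sites "will enroll about 17,500 cases of cardiac arrest and about 13,000 cases of trauma with impaired physiology in the field annually". The planning outcome rates are given next: "Estimated survival to discharge will be 5.57% after cardiac arrest. Estimated mortality will be 16.55% after trauma with impaired physiology in the field". On the strength of these figures it claims "88%, 90%, 99% and 91% power to detect risk differences of 2.5/100,000 in the annual rate of cardiac arrest". The three other differences to which those powers refer are "2.5/100,000 in the annual rate of traumatic injury, 1% in survival to discharge after cardiac arrest, and 1.5% in mortality after traumatic injury". Hypotheses 2a and 2b frame the comparison as one year against another.

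Table 1 in Section C gives the site estimates behind these figures. Its totals are 23,709,328 people, 17,466 arrests, 13,082 included trauma cases and 10,331 trauma survivors. It prints no total for arrest survivors and no pooled rate. Two rows matter here:

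- Pittsburgh, included trauma: 770 cases, 129 survivors, 83.3% mortality. The other ten sites run from 9.7% to 28.6%.
- Milwaukee, cardiac arrest: 59 survivors of 1,062, printed as 4.4%.

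Section B, on variation in outcome, puts the spread of trauma mortality across sites at somewhat over a factor of two.

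**The concern.** The overview presents its powers as consequences of the rates given just before them, so a reader should be able to recompute them. For trauma incidence that fails: 13,000 cases in 24.5 million is a much lower rate than 90% power implies, and a lower rate gives higher power for the same absolute difference.

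The planning mortality also conflicts with its own source table. Table 1's totals imply 21.0% and the text uses 16.55%. Specific Aim 2 is to define incidence and outcome, and Table 1 is presented as the baseline. Anyone who reuses its trauma total would carry forward a mortality that the protocol's text does not use.

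**Working it through.** **Inputs.** Cases, population, rates and differences are from the Section A overview; site rows and totals are from Table 1. The significance level is not in the text available. I assume 5% two-sided and two equal years.

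**Formula.** Power = Φ(δ/SE − 1.96). For incidence, SE = √[(r₁ + r₂)/N], with N people in each year. For proportions, SE = √[(p₁q₁ + p₂q₂)/n], with n cases in each year. Ranges cover an increase and a decrease of δ.

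**1. Where the stated 90% comes from.** The 11 site trauma rates in Table 1 sum to 808, and 808/11 = 73.5 per 100,000. With 24.5 million people, SE = 0.781 (increase) or 0.768 (decrease) per 100,000. Then 2.5/0.781 = 3.20 gives 89.3%, and 2.5/0.768 = 3.26 gives 90.3%. This reproduces 90%. The implied cases are 73.5 × 245 ≈ 18,000.

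**2. What the stated inputs give.** 13,000/24.5 million = 53.1 per 100,000. SE = 0.666 or 0.650; 2.5/SE = 3.75 or 3.84; power 96.4% to 97.0%. From the Table 1 totals, 13,082/23,709,328 = 55.2 per 100,000. SE = 0.690 or 0.674; power 95.2% to 96.0%.

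Another significance level does not rescue the figure. One-sided 5% gives about 98 to 99%. Two-sided 1% gives 88 to 90% for trauma incidence, but only 75 to 77% for arrest incidence, where the protocol states 88%.

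**3. Arrest survival rate.** The 11 printed percentages sum to 61.3, and 61.3/11 = 5.573%, the stated 5.57%. The pooled rate is 929/17,466 = 5.32%. Milwaukee's counts give 59/1,062 = 5.56%, not 4.4%; conversely, 4.4% of 1,062 is about 47. With 5.56% in place of 4.4% the plain mean is (61.3 − 4.4 + 5.56)/11 = 5.68%.

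**4. Trauma mortality rate.**

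- Plain mean as printed: 248.6/11 = 22.60%.
- With Pittsburgh at 100 − 83.3 = 16.7%: (248.6 − 83.3 + 16.7)/11 = 182.0/11 = 16.55%, the stated figure. Omitting Pittsburgh gives 165.3/10 = 16.53%.
- Printed totals: (13,082 − 10,331)/13,082 = 21.0%.
- Pooled, with 129 read as deaths (641 survivors): the rows sum to 13,083 cases and 10,332 − 129 + 641 = 10,844 survivors, so 2,239/13,083 = 17.1%.
- Spread across sites: 83.3/9.7 = 8.6-fold as printed; 28.6/9.7 = 2.9-fold with the row swapped. Only the second fits the description in Section B.

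**5. The other three powers.**

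| Comparison | Stated | From stated inputs | From Table 1, pooled |
|---|---|---|---|
| Arrest incidence, 2.5/100,000 | 88% | 90.1–91.1% (71.4/100,000) | 88.2–89.2% (73.7/100,000) |
| Arrest survival, 1 point | 99% | 97.5–98.9% (5.57%) | 97.9–99.2% (5.32%) |
| Trauma mortality, 1.5 points | 91% | 89.2–91.2% (16.55%) | 88.6–90.7% (17.1%, row swapped); 83.6–85.5% (21.0%, as printed) |

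**The case against.** The best reply is that little turns on this. Three of the four powers reproduce, the fourth is understated, the registry takes every eligible case, and the protocol calls the Table 1 figures best estimates because data were not readily available at every site. All of that stands, and it limits the severity.

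The Sample Size text is also absent from the copy reviewed: the contents list the section, and only figure captions and a closing paragraph remain. The significance level, the formula and the way the rates were averaged may be stated there. Unweighted averaging is therefore an inference from numerical agreement. The 88% for arrest incidence adds no support to it, since the unweighted mean (76.1 per 100,000 in 24.5 million) and the Table 1 totals give the same power.

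The two populations are not in themselves an error. One is a rounded expectation and the other sums site estimates from sampling years between 1999 and 2004; they differ by about 3%. But the stated case numbers follow the Table 1 totals, so a case count from one source sits beside a population from another.

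A reader might infer that the planning mortality was built on an inverted row. The figures point the other way: 16.55% fits 129 deaths, and the probable slip is in the printed table and its total.

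**Conclusion.** The point holds in a limited form.

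- **One stated power is wrong for its stated inputs.** Trauma incidence has about 96 to 97% power from the overview's figures, or 95 to 96% from the Table 1 totals, not 90%. This rests on a year-against-year comparison at two-sided 5%.
- **Table 1 contradicts the text on trauma mortality.** It implies 21.0% against 16.55%. This needs no assumption about the test. That the 129 are deaths is likely, but only the site can confirm it.
- **Milwaukee's arrest row is internally inconsistent.** Either the count or the percentage may be wrong.
- **The planning rates appear to be unweighted site means.** Pooling moves survival from 5.57% to 5.3%, and mortality from 16.55% to 17.1% with Pittsburgh swapped. The effect on power is about half a point.

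A reader might conclude that none of the powers follows from the inputs, or that the registry is underpowered. Neither is supported. Survival and mortality power reproduce from the stated rates and cases, arrest incidence reproduces from the Table 1 totals, and the one failing figure is too low. Trauma-mortality power falls to about 84 to 85% only if the printed Pittsburgh row is correct. This is a should-fix correction.

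**What to change.** 1. Verify with the sites the Pittsburgh trauma row (129 survivors or 129 deaths) and the Milwaukee arrest row (count and percentage). Correct the rows and the Table 1 totals.
2. Derive the planning rates as pooled counts over pooled denominators, with cases and population from the same source. On present figures these are 73.7 arrests and 55.2 trauma cases per 100,000, about 5.3% arrest survival and, if Pittsburgh is swapped, 17.1% trauma mortality.
3. Restate the trauma-incidence power (about 95 to 97%), and recompute the other three powers and the power figures from the same inputs, giving the significance level and the averaging method beside them.

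The cost is two site queries, a corrected table and a few sentences. Design, enrolment and data collection do not change.
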